## 10 SAFETY ANALYSES

The safety analysis will be performed using the Safety Population. Safety parameters include adverse events (AEs), laboratory parameters, vital signs, infections, assessment of tumor progression, and assessment of mortality and assessment of progression-free survival.

#### 10.1 ADVERSE EVENTS

Adverse events will be coded using MedDRA version 20.0. An overall summary of AEs will present the frequency and percentage of patients with AEs, treatment-emergent AEs (TEAEs), TEAEs leading to discontinuation of study, TEAEs leading to death, and SAEs. A TEAE is defined as an AE that is new in onset or aggravated in severity or frequency following the first study drug administration and reported between randomization through the 6 week post-RT visit or 4 weeks post last study drug infusion, whichever is longer. An SAE is defined as an AE that results in any of the following outcomes:

- Death
- A life-threatening AE

- Prolongation of existing hospitalization or subsequent need for hospitalization
- A persistent or significant disability/incapacity
- A congenital anomaly/birth defect
- A medical or surgical intervention to prevent one of the above

The number and percentage of patients reporting TEAEs in each treatment group will be tabulated by (1) SOC and PT, (2) by SOC, PT, and severity, and (3) by SOC, PT, and relationship to study drug. If more than one event occurs with the same preferred term for the same patient, the patient will be counted only once for that preferred term using the most severe and most related occurrence for the summarization by severity and by relationship to the study drug, respectively. AEs with missing severity and relationship to the study drug will be treated as "severe" and "related" respectively. In addition, the number and percentage of patients reporting SAEs in each treatment group will be tabulated by SOC and PT. AEs that started before the first study drug administration will be included in listings but not in summaries.

If there are any missing dates for AEs, please see Appendix 1 for data handling conventions.

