6. INVESTIGATIONAL PLAN

6.1. Overall Study Design and Plan: Description

Approximately 260 patients will be enrolled into this Phase 3, placebo-controlled, double-blind, multinational study to evaluate the efficacy of SGX942 compared to placebo in treating the duration of SOM in patients receiving CRT for the treatment of head and neck cancer. Patients will be randomized into one of two groups (1.5 mg/kg SGX942:Placebo) at a 1:1 ratio. They will be stratified by site, presence of gastrostomy tube, and HPV status. Patients will receive their initial blinded IV study drug (1.5 mg/kg SGX942 or placebo) within 3 days of starting radiation.

The primary efficacy outcome for this study is the duration of SOM, defined as the number of days from the first oral examination with a WHO Grade assessment of 3 or 4 through the first day that a WHO Grade of ≤ 3 is recorded with no subsequent assessments ≥ 3 . OM will be evaluated using the WHO scoring for OM.

Patients will be screened to assess their eligibility prior to randomization. After randomization, subjects will begin treatment with study drug within 3 days of initiating RT.

Patients will receive study drug while undergoing CRT and continue to receive study drug for 2 weeks after the completion of their RT. Study visit days will be every third day (± 1 day). On study visit days, patients will receive the 4-minute infusion of study drug. Study drug will not be given on the same day as chemotherapy. Study drug can be given at any time during the visit day, but must occur on the same calendar day that is the study visit day. The study visit calendar extends to 2 weeks post-completion of RT.

Efficacy will be further assessed at the 3 through 6 weeks post-RT completion visits. Follow-up visits will be conducted at 12 weeks and 12 months after the last radiation dose to continue to evaluate safety and secondary endpoints.

Below is a table outlining the study schedule of procedures and assessments. The study week designations assume a 7-week CRT schedule. These times may require adjustment (as described below) if the treatment course is shorter or if treatment breaks prolong the CRT for more than 7 weeks.

Confidential

Table 7: Schedule of Events by Week

Study week	Screen	Base ²	1w ³	2w	3w	4w	5w	6w	7 w	8w	9w	10w	11w	12w	13w	15- 55 w	19w	59w
Post-RT ¹										1w	2w	3w	4w	5w ⁴	6w	2m-11 m ⁵	12w	12m
Medical History	X	X	2X	2X	2X	2X	2X	2X	2X	2X	2X	X	X	X	X	X	X	X
Informed Consent	X																	

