11.1.1 Assessment of AEs

Site personnel will question and record in the eCRF all reported AEs, as defined in Section 11.2.1 that are reported between randomization through the 6 week post-RT visit. The PI will assess of the severity of the AE using the CTCAE criteria (Appendix 1). The AEs will be coded as to preferred terminology, and body system using the Medical Dictionary for Regulatory Activities (MedDRA) using a computer auto-coder and all assignments reviewed by a blinded medical reviewer. The number of events and the number of patients with each event defined by the preferred term and by body system category will be presented. Additional tables will compare the reported AEs by preferred term and body system classification classified by CTCAE severity grade (1-5) and separately by PI assessment of relationship to study drug.

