11.2. Safety Parameters

11.2.1 Adverse Experience (AE)

Any noxious or unintended event that occurs in association with the use of an investigational agent in humans, whether considered related to the investigational agent or not. This definition encompasses symptoms or signs reported by the subject or detected by the investigator or other competent observer, as well as medically important deviations from normality in the results of ancillary investigations. If present at time of first dose of study drug, such AEs must be recorded as part of the medical history.

Treatment-Emergent Adverse Experience: An AE that is new in onset or aggravated in severity or frequency following entry into the study. In addition, any pathological finding on physical examination or diagnostic procedure that is new in occurrence or exacerbated in comparison with the subject's status at study entry is considered a treatment-emergent AE if it requires any medical or surgical intervention whatsoever (including, but not limited to, additional diagnostic procedures or alteration of prescribed therapy).

All AEs, whether judged to be related or not to the study drug, should be recorded in both the medical record and the eCRF. The start and resolution dates, the judgment of the severity of the AE, the judgment of the relationship of the AE to the study drug, the action taken for subsequent dose of study drug, and the outcome should be noted.

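### SAP 10.1 counts events that worsen after the first dose as treatment-emergent, then keeps every event that began before that dose out of all summaries

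*SAP*

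**What the plan says.** SAP 10.1 sets the definition: "A TEAE is defined as an AE that is new in onset or aggravated in severity or frequency following the first study drug administration". It plans tables of treatment-emergent events by system organ class and preferred term, by severity, and by relationship to study drug. The overall summary shows patients with any AE separately from patients with a treatment-emergent AE. For serious events, "the number and percentage of patients reporting SAEs in each treatment group will be tabulated by SOC and PT". The last rule in that section on what is tabulated reads: "AEs that started before the first study drug administration will be included in listings but not in summaries".

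The protocol is wider. Its treatment-emergent definition (11.2.1) runs from study entry, not first dose: "An AE that is new in onset or aggravated in severity or frequency following entry into the study". Sections 11.1.1 and 11.1.2 cover AEs and SAEs reported from randomization to the 6-week post-RT visit, and for AEs promise: "The number of events and the number of patients with each event defined by the preferred term and by body system category will be presented". Sections 11.5.1 and 11.5.2 require events after enrollment but before treatment to be recorded in the eCRF. Section 11.2.1, however, says of events by the first dose: "If present at time of first dose of study drug, such AEs must be recorded as part of the medical history".

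**The concern.** An event can be aggravated after the first dose only if it already existed. The closing rule removes exactly the events that the aggravation half of the definition was written to capture. If a programmer follows it literally, that half of the definition never reaches a table.

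At stake is the safety comparison against a background of chemoradiation toxicity, where one plausible form of harm from an added drug is the worsening of events already under way. If study drug did this, more worsened events would be omitted from the active arm than from placebo, and the tables would lean towards no difference. Applying the rule equally to both blinded arms does not prevent that.

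**Working it through.** The plan states no figure to reproduce, so the check compares texts and then measures the window.

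**1. Where each kind of event goes under SAP 10.1, read literally**

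| Event | Meets SAP treatment-emergent definition? | In summaries? |
|---|---|---|
| Starts after first dose | Yes | Yes |
| Starts before first dose, unchanged | No | No |
| Starts before first dose, worsens later | Yes (aggravated) | No |
| SAE starting between randomization and first dose | Not relevant to the SAE table | No |

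The third row is the contradiction. The fourth is a gap against Protocol 11.1.2, whose period starts at randomization. The closing rule also nearly empties the distinction between the AE and treatment-emergent AE lines of the overall summary, since few events could count in one and not the other.

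**2. Whether another passage resolves it**

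Protocol 11.2.1 asks for start and resolution dates, severity, relationship, action taken and outcome for each AE. It does not say whether a worsening is a new entry or an update to the existing one. An event that begins after randomization and is still present at first dose has two prescribed destinations: the AE record (11.5.1) and the medical history (11.2.1). Neither passage says what happens when it later worsens.

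**3. Length of the window**

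Protocol 6.3.2 places randomization and the start of AE collection at Baseline, within 96 hours (4 days) of the first dose. The protocol synopsis expects 6 to 11 weeks of study drug, ending 2 weeks after RT. AE collection continues to the 6-week post-RT visit, 4 weeks later.

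- Shortest course: (6 + 4) × 7 = 70 days from first dose; 4 / (4 + 70) = 5.4%.
- Longest course: (11 + 4) × 7 = 105 days; 4 / (4 + 105) = 3.7%.

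**4. What the window can contain**

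Study drug may start up to 3 days after RT begins, and "Study drug will not be given on the same day as chemotherapy" (Protocol 6.1). The schedule of events shows cisplatin in Week 1, with timing left to the treating physicians. If cisplatin is given first, its acute effects and those of the first radiation fractions can begin before the first study-drug dose.

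**The case against.** The best defence is that the two SAP sentences can coexist. If the condition before the first dose goes to medical history and its worsening is entered as a new AE with its own later start date, the exclusion removes only the earlier record. SAP 10.1 expects repeated occurrences of one preferred term per patient and keeps the most severe, and Protocol 11.5.1 refers to form-completion guidelines that are not among these documents. This reading is workable, but neither document states it, and the SAP should not depend on it.

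Several limits on the consequences do stand. A reader might infer that SAEs starting before the first dose are lost. They are not: they stay in listings, are reportable within 24 hours (Protocol 11.5.2) and are to have narratives in the study report (11.1.2). Laboratory shift tables, vital signs, infections by grade and mortality are specified separately, so renal and haematological changes would largely show there. Wholly missing AE start dates are set to the first-dose date (SAP Appendix 1), which keeps those events in the summaries. None of these, however, gives a between-arm comparison of worsened clinical events such as nausea.

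It is also fair to say that an SAE with onset before the first dose cannot have been started by study drug. That supports showing such SAEs separately, not omitting them.

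**Conclusion.** SAP 10.1 contradicts itself for events that start before the first dose and worsen or become serious afterwards, and it is narrower than the protocol on the AE and SAE period and on the treatment-emergent anchor. This conclusion rests on the wording alone. The consequence, that such events could be missing from the treatment-emergent, severity, relationship and SAE tables, assumes the literal rule is programmed and a worsened event keeps its original start date.

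The size is unknown. The window is at most about 4 days, and no document says how many events begin in it or later worsen. Assuming that 20% to 40% of patients have a continuing event starting in the window, and that 10% to 30% of those worsen, gives 130 × 0.20 × 0.10 = 2.6 to 130 × 0.40 × 0.30 = 15.6 patients per arm. A reader might take that as an estimate, but neither rate has any basis in the documents and it should not be used as one.

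A reader might also infer that the plan conceals toxicity caused by the drug. The documents do not support that: the rule would equally drop worsening due to chemoradiation or cancer, in either arm. What is shown is a stated rule that is wrong as written and could bias the tables towards no difference if the drug does aggravate existing events.

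**What to change.** In SAP 10.1, limit the exclusion to AEs that started before the first dose and did not afterwards worsen in grade or frequency or become serious. Count a worsened event as treatment-emergent, and state in the SAP and the form-completion instructions that a worsening is a new AE entry dated at the worsening. Without that date the post-dose grade cannot be derived, so say how events already held on a single record will be handled. Tabulate SAEs from randomization, with those starting before the first dose shown separately.

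Then reconcile the two documents on three points: the treatment-emergent anchor (study entry or first dose), the medical-history rule in Protocol 11.2.1 for events arising after randomization, and the SAE presentations by grade and relationship that Protocol 11.1.2 describes (in an incomplete sentence) but SAP 10.1 omits.

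The cost is one derivation in the AE dataset, wording in the SAP and protocol, possible queries on single-record events, and slightly higher AE counts in both arms. No efficacy analysis changes.

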#### 10.2 CLINICAL LABORATORY PARAMETERS

Descriptive statistics for laboratory values (in SI units) and changes from baseline at each assessment time point will be presented by treatment group for the following laboratory parameters:

- Serum pregnancy test: human chorionic gonadotropin (HCG)
- Hematology: red blood cell count (RBC), hematocrit, hemoglobin, RBC indices, platelet count, white blood cell count (WBC), and WBC differential count
- Chemistry: serum sodium, serum potassium, serum chloride, serum bicarbonate (CO2), alanine aminotransferase (ALT), aspartate aminotransferase (AST), total bilirubin, alkaline phosphatase, total protein, serum creatinine, and blood urea nitrogen (BUN)

Laboratory values will be classified as "normal", "low", or "high" based on the central laboratory's normal ranges. Shift tables for each parameter will be tabulated by treatment group.

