7.2. Subject Exclusion Criteria

Patients with any of the following criteria are **NOT** eligible for enrollment:

- 1. Current mucositis
- 2. Current clinically significant active infection that in the opinion of the Investigator would make them an unfit participant in the trial
- 3. Planned to receive Erbitux[™] (Cetuximab) or similar targeted therapy between baseline and 6 weeks post-radiation therapy
- 4. Current use of prohibited therapies listed in Section 8.2
- 5. Prior radiation to the head and neck
- 6. Chemotherapy treatment within the previous 12 months
- 7. Tumors of the lips, sinuses, salivary glands, nasopharynx, hypopharynx, or larynx
- 8. Evidence of significant renal, hepatic, hematologic, or immunologic disease determined by any one of the following: (the below are examples of evidence of significant disease, not required tests)
 - a. Estimated creatinine clearance <30 mL/min
 - b. ALT or AST level greater than 10-fold the upper limit of normal or total bilirubin greater than 3-fold the upper limit of normal
 - c. Manifestations of end-stage liver disease, such as ascites or hepatic encephalopathy
 - d. Thrombocytopenia (less than 60,000 cells/mm³)
 - e. CD4⁺ T cell count below 200 cells per μL (verification only required if there is a clinical diagnosis of HIV infection)
- 9. Evidence of immediate life-threatening disease or a life expectancy of less than 3 months
- 10. Women who are pregnant or breast-feeding
- 11. Participation in any study involving administration of an investigational agent within 30 days of randomization into this study
- 12. Any condition that, in the opinion of the Investigator, would compromise the safety of the subject or quality of the data

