11.1.3 Assessment of Laboratory and Vital Signs

Each of the laboratory tests outlined in Section 6.2.5 and each of the vital signs outlined in Section 6.2.6.4 will be summarized for each collection period by treatment group as:

Group mean

Original: 11 January 2017

- Group standard deviation
- Group median
- Group range

Additionally, each evaluation will be summarized as a change from baseline for each patient by treatment group as:

- Group mean
- Group standard deviation
- Group median
- Group range

Using the Central Laboratory's normal ranges and standard table of normal vital signs, each assessment will be classified as "normal", "low", or "high" and shift tables for each parameter shown of each assessment by treatment group will be displayed.

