11.4. Severity of Adverse Event

A clinical determination of the intensity of an AE should be done for all reported AEs. The severity assessment should use the CTCAE grading system that assesses the severity of each AE from grades 1-5. The grading system can be found in Appendix 1.

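### Laboratory shift tables have only low, normal and high levels, so no laboratory table counts patients with marked worsening by arm

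*SAP*

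**What the plan says.** SAP section 10.2 sorts laboratory values into low, normal or high by the central laboratory's "normal ranges. Shift tables for each parameter will be tabulated by treatment group". Protocol section 11.1.3 uses the same three classes and adds that "shift tables for each parameter shown of each assessment by treatment group will be displayed". For laboratory data, neither document plans toxicity grades, multiples of the limit of normal, a worst post-baseline category, or a count of marked abnormalities.

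Three other parts of the plan bear on the point:

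- **Descriptive statistics.** SAP 10.2 also summarises values and changes from baseline at each time point by arm. SAP 3.3 gives the statistics as n, mean, SD, median, minimum and maximum. Protocol 11.1.3 lists mean, SD, median and range, both for the values and for each patient's change.
- **Adverse events.** Protocol 11.2.1 counts medically important abnormal test results as adverse events. Protocol 11.4 says "The severity assessment should use the CTCAE grading system that assesses the severity of each AE from grades 1-5". SAP 10.1 counts patients by system organ class, preferred term and severity, at their most severe occurrence.
- **Entry limits.** Protocol 7.2 lists "ALT or AST level greater than 10-fold the upper limit of normal or total bilirubin greater than 3-fold the upper limit of normal" and platelets below 60,000 per mm³ among the signs of excluding disease, with the note "the below are examples of evidence of significant disease, not required tests".

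**The concern.** The effect of SGX942 on safety laboratory values is a stated objective (Protocol 5.3, SAP 1.3). Protocol 8.2 has all patients on cisplatin at 80-100 mg/m² alongside radiation. If chemoradiation itself moves laboratory values in both arms, the question about SGX942 is whether it makes those changes deeper. A three-level table records only whether a value crosses a limit of the normal range. It does not record how far the value goes.

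At stake is whether the final report would show, by arm and from the central laboratory data, how many patients had a severe change.

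**Working it through.** The plan states no figure on this point, so there is nothing to reproduce. The check applies the planned displays to illustrative values.

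**Step 1: the shift table.** ALT and bilirubin are expressed in multiples of the upper limit of normal, so high means above 1. The documents do not give the lower limit for platelets. I assume 130,000 to 150,000 per mm³; the cells below hold across that range, except that the 129,000 row uses 130,000.

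| Parameter | Baseline | Later value | Change | Cell |
|---|---|---|---|---|
| ALT | 0.8 | 1.1 | +0.3 | normal to high |
| ALT | 0.8 | 15 | +14.2 | normal to high |
| ALT | 1.1 | 10 | +8.9 | high to high |
| ALT | 9.9 | 30 | +20.1 | high to high |
| Bilirubin | 2.9 | 9 | +6.1 | high to high |
| Platelets | 200,000 | 129,000 | −71,000 | normal to low |
| Platelets | 200,000 | 10,000 | −190,000 | normal to low |
| Platelets | 60,000 | 10,000 | −50,000 | low to low |

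Mild and severe changes share a cell whether the baseline is normal or abnormal.

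**Step 2: one extreme patient in the descriptive statistics.** Take one arm of 130 (Protocol synopsis). Simulate 129 ALT changes with mean 0 and an assumed SD of 0.3 times the upper limit, then add one patient with +20.1.

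- Maximum change: 0.72 becomes 20.1.
- Mean change: −0.011 becomes (129 × −0.0108 + 20.1)/130 = 0.144.
- Median change: 0.002 becomes 0.003.

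The planned maximum shows the extreme case clearly.

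**Step 3: a difference in the number of severe cases.** Assume 3 of 130 patients in one arm and 12 of 130 in the other have platelets 100,000 lower than they would otherwise be (for example 20,000 instead of 120,000). Assume also that the lowest value and the largest fall are the same in both arms.

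- Shift table: 20,000 and 120,000 are both low, so the cell counts do not change.
- Minimum and range: the same in both arms by assumption.
- Median: moves little, since at most 12/130 = 9.2% of an arm is affected.
- Mean: differs by (12 − 3) × 100,000/130 = 6,923. With an assumed SD of 60,000 to 80,000 this is 0.12 to 0.09 SD. The standard error of the difference is SD × √(2/130) = 7,442 to 9,923, so the difference is 0.93 to 0.70 standard errors.

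A count by arm would show 2.3% against 9.2%, a difference of 9/130 = 6.9 percentage points. The simple Wald standard error is √(0.0231 × 0.9769/130 + 0.0923 × 0.9077/130) = 0.0286, giving a 95% CI of about 1.3 to 12.5 points. With 3 events in one arm this interval is only a rough guide.

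**Step 4: the adverse event route.** Graded counts exist here, but a laboratory change must first be reported as an event.

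- Protocol 11.5.1 relies on spontaneous reports or a general, undirected conversation.
- Protocol 11.2.1 treats a worsened diagnostic finding as treatment-emergent if it needed some intervention. It sends events already present at the first dose to medical history.
- SAP 10.1 counts aggravated events as treatment-emergent, but keeps events that began before the first dose out of the summaries.

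Capture is therefore least certain for patients whose values were already abnormal.

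**The case against.** The strongest reply is that the shift table is one display among several. The minimum, maximum and change-from-baseline statistics expose an extreme value, as Step 2 shows. Medically important laboratory changes qualify as adverse events, are graded under the protocol, and are counted by patient, arm and severity. Protocol 11.6 has the DMC review laboratory adverse events and lets it request laboratory values. The two documents agree on the method, and the table shells are a separate document (SAP Introduction) that may contain more. All of this stands, and it makes the point a minor one.

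It does not close the gap. A maximum describes one patient, the adverse event count depends on reporting, and the DMC section sets out no graded table for the final analysis.

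A reader might infer three stronger conclusions that the documents do not support:

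- *Severe worsening cannot be seen in the planned output.* This is true of the shift table alone.
- *A harmful effect would leave the shift tables identical in the two arms.* That requires no extra patient to cross a range limit. An effect that pushes more patients out of range, or delays their return across the scheduled samples, changes the cell counts.
- *The problem arises because patients with abnormal values may enter.* Step 1 shows the same loss from a normal baseline. The limits in Protocol 7.2 are examples under a wider exclusion for significant disease, investigators have further discretion, and the documents do not say how many patients enter outside normal.

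**Conclusion.** The point holds in a limited form. The laboratory shift tables cannot separate mild from severe worsening at any baseline, and no planned laboratory table counts patients with marked worsening by arm. Such counts would come only from adverse events that investigators chose to report.

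The size in this trial cannot be computed, because the documents give neither the distribution of baseline values nor the expected frequency of severe changes. Steps 2 and 3 are illustrations. They rest on an assumed platelet limit, assumed SDs, assumed case numbers and, in Step 3, equal extremes in the two arms. They show what each display can and cannot reveal, not what will happen.

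This is a cheap improvement to the reporting of a stated safety objective. It does not affect the primary analysis, the sample size or the error rate.

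**What to change.** In SAP section 10.2, keep the low/normal/high tables and add, for each parameter that has a CTCAE grade:

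1. A shift table by arm from baseline CTCAE grade to worst post-baseline CTCAE grade. The grade is taken from the central laboratory values, using the CTCAE version in Protocol Appendix 1.
2. The number and percentage of patients by arm whose grade rises to 3 or above, including a rise from 3 to 4, with the between-arm difference and 95% CI, labelled descriptive. The SAP should name an interval method suited to small counts.

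Parameters without a grade stay with low/normal/high only.

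The data are already planned: samples at Weeks 3 and 6 and at 2, 4 and 6 weeks after radiation (Protocol 6.2.5.2 and 6.2.5.3). The worst grade will be the worst among those samples, so a change between visits can still be missed. The cost is SAP wording, programming, a few more tables, and several safety comparisons without multiplicity adjustment, which is why they should be labelled descriptive. Sites and patients do nothing extra.
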